7.2.3 Demographic and Other Baseline Characteristics

Demographic and other baseline characteristics will be summarized by descriptive statistics.

Number and percentage of subjects randomized in each country and site will be presented by treatment group for the SAF.

Those subjects randomized to Mirabegron will start at 25 mg and may increase to 50 mg after 4 weeks or 8 weeks based on individual subject efficacy, tolerability and Investigator discretion. Those subjects randomized to PBO will start blinded product matched to the Mirabegron 25 mg tablet and may also increase to 50 mg PBO after 4 or 8 weeks. Once a patient has increased dose, they will remain on that dose for the remainder of the study unless for safety reasons that require discontinuation of study drug.

Descriptive statistics for age, weight, body mass index (BMI) and height at study entry will be presented. Frequency tabulations for sex, ethnicity, age group (<75, >=75) and race will be presented. This will be done for the SAF, FAS-I and PPS by treatment group.

Demographic variables are based on the last available value prior to first dose of double-blind treatment.

BMI is calculated as $BMI (kg/m^2) = \text{weight (kg)} / \text{height}^2 (m)$.

OAB related baseline characteristics summarized in Table 6 and recorded on the eCRF from the Screening Visit will be summarized for the FAS-I, and PPS, by treatment group.

Duration of the OAB symptoms in months is calculated as the number of months from onset date of OAB symptoms at diagnosis to the informed consent date at the screening.

$$(\text{Date of Informed Consent} - \text{onset date of OAB symptoms at diagnosis} + 1) / 30.44$$

Table 6 OAB Related Baseline Characteristics from eCRF

Characteristic	Summarized as	Categories
Duration of OAB symptoms (in months)	Continuous	N/A
OAB Symptoms	Categorical	
• Urgency Incontinence Only• Mixed Stress/Urgency Incontinence With Urgency as a Predominant Factor• Frequency/Urgency Without Incontinence

Characteristic	Summarized as	Categories
Number of previous OAB medications (prior to screening) group	Categorical	
 • 0 • 1 • >=2
OAB Severity at Baseline Based on Number of Micturition per 24 hours	Categorical	
 • <8 • 8-<10 • >=10 - <=15 • >15
OAB Severity at Baseline Based on Number of Incontinence Episodes per 24 hours	Categorical	
 • >0 - <=2 • >2 - <4 • >=4
Type of OAB at Screening	Categorical	
 • Urgency Incontinence Only • Mixed Stress/Urgency Incontinence with Urgency as Predominant Factor
Previous OAB Medication	Categorical	
 • Yes • No
Effectiveness of Previous OAB Medication	Categorical	
 • At Least One Effective • None Effective
Discontinuation of Previous OAB Medication Due to Insufficient Effect	Categorical	
 • Yes • No
Discontinuation of Previous OAB Medication Due to Poor Tolerability	Categorical	
 • Yes • No
Previous Treatment with Solifenacina	Categorical	
 • Yes • No
Previous Treatment with Mirabegron	Categorical	
 • Yes • No
Previous non-drug treatment for OAB (prior to screening)	Free Text	
 • Yes 
 →Biofeedback →Exercises →Electrical Stimulation →Behavioral →Pessaries →Implants →Surgery • No

OAB related baseline characteristics derived from the 3-day micturition diary prior to the Run-in Visit and the Randomization Visit will be summarized as continuous variables overall for the FAS-I, and PPS with following listed characteristics in Table 7. Only patients with a baseline value > 0 will be included in each individual summary.

Table 7 OAB Related Baseline Characteristics from 3-Day Micturition Diary

Characteristic	Summarized as	Categories
Number of incontinence episodes reported during the 3-day diary	Continuous	N/A
Mean number of incontinence episodes per 24 hours	Continuous	N/A
Number of urgency incontinence episodes reported during the 3-day diary	Continuous	N/A
Mean number of urgency incontinence episodes per 24 hours	Continuous	N/A
Mean number of micturitions per 24 hours	Continuous	N/A
Number of pads reported during the 3-day diary	Continuous	N/A
Mean number of pads per 24 hours	Continuous	N/A
Mean number of urgency episodes (grade 3 or 4) per 24 hours	Continuous	N/A
Number of nocturia episodes reported during the 3-day diary	Continuous	N/A
Mean number of nocturia episodes per 24 hours	Continuous	N/A

Medical history is coded in MedDRA, and will be summarized by System Organ Class (SOC) and Preferred Term (PT) as well as by PT alone, by treatment group for the SAF.

7.2.4 Previous and Concomitant Medications

Previous medications are coded with World Health Organization – Drug Dictionary (WHO-DD), and will be summarized by therapeutic subgroup (Anatomical Therapeutic Chemical (ATC) 2nd level) and chemical subgroup (ATC 4th level) and preferred World Health Organization (WHO) name by treatment group for the SAF.

As with previous medication, concomitant medication will be summarized for each treatment group by therapeutic subgroup (ATC 2nd level) and chemical subgroup (ATC 4th level) and preferred WHO name for the SAF. Subjects taking the same medication multiple times will be counted once per medication and investigational period. A medication that can be classified into several chemical and/or therapeutic subgroups is presented in all chemical and therapeutic subgroups.

7.3 Study Drugs

7.3.1 Exposure

The following information on drug exposure will be presented for each treatment group for the SAF:

- Descriptive statistics for number of days treatment was received will be presented by treatment group
- Number and percent of subjects with dose increase from 25mg to 50mg by treatment group. Overall and split by those whose dose increased at 4 weeks versus 8 weeks.

Duration of exposure will be summarized in two ways.

- Descriptive statistics will be presented by treatment group.
- Counts and percentages of exposure time will be categorized according to the following categories by treatment group:

- 1 to 6 days
 - 7 to 13 days
 - 14 to 27 days
 - 28 to 55 days
 - 56 to 83 days
 - 84 days or more
 - Unknown.
- Counts and percentages of cumulative exposure will be categorized according to the following categories by treatment group:
 - ≥ 7 days
 - ≥ 14 days
 - ≥ 28 days
 - ≥ 56 days
 - ≥ 84 days

Counts and percentages of subjects in each of these categories will be summarized for each treatment group for the SAF.

7.3.2 Treatment Compliance

Overall compliance will be examined for subjects in the SAF whose total study drug count and first and last days of treatment are known.

Percent overall compliance will be summarized in two ways for the SAF:

- Descriptive statistics will be presented by treatment group.
- Percent compliance will be categorized according to the following categories by treatment group:
 - less than 50%
 - at least 50%, less than 70%
 - at least 70%, less than 90%
 - at least 90%, less than 110%
 - greater than 110%
 - Unknown.

7.4 Analysis of Efficacy

7.4.1 Analysis of Primary Endpoints

The primary analysis set for efficacy analyses will be the FAS-I. The co-primary efficacy variables are Change from baseline to end of treatment in mean number of micturitions per 24 hours based on a 3-day micturition diary and Change from baseline to end of treatment in mean number of incontinence episodes per 24 hours based on a 3-day micturition diary.

A step-down gatekeeping procedure will be performed to control the type I error rate at the 0.05 significance level for the multiple endpoints of the co-primary efficacy variables of change from baseline to end of treatment in mean number of micturitions per 24 hours and mean number of incontinence episodes per 24 hours and the key secondary efficacy variable of change from baseline to end of treatment in mean volume voided per micturition. The hypotheses will be tested in the following order: mean number of micturitions per 24 hours, mean number of incontinence episodes per 24 hours and mean volume voided per micturition.

If the two co-primary endpoints are statistically significant at the same alpha level ($\alpha = 0.05$), the secondary endpoint of mean volume voided per micturition will then be carried out.

Mean number of micturitions per 24 hours

The hypothesis being tested for the mean number of micturitions per 24 hours can be stated as;

H0: Mean change from baseline in number of micturitions per 24 hours at end of treatment is the same for placebo and Mirabegron.

H1: Mean change from baseline in number of micturitions per 24 hours at end of treatment is different for placebo and Mirabegron.

Change from baseline to end of treatment in mean number of micturitions per 24 hours will be tested using an ANCOVA model. The response variable will be the mean change in number of micturitions episodes per 24 hours from baseline to the end of the study with treatment group, gender, and age group (<75 , ≥ 75) as fixed factors and baseline mean number of micturitions episodes per 24 hours as the covariate in the model. As part of the ANCOVA results, LS means and two-sided 95% CIs for mean changes from baseline within each treatment group will be provided. Differences in LS means between Mirabegron and placebo will be derived together with 95% CIs and p-values.

Mean number of incontinence episodes per 24 hours

The hypothesis being tested for the mean number of incontinence episodes per 24 hours can be stated as;

H0: Mean change from baseline in number of incontinence episodes per 24 hours at end of treatment is the same for placebo and Mirabegron.

H1: Mean change from baseline in number of incontinence episodes per 24 hours at end of treatment is different for placebo and Mirabegron.

In order to test for statistical differences in Change from baseline to end of treatment in mean number of incontinence episodes per 24 hours between Mirabegron and placebo, a stratified rank ANCOVA will be used. The response variable is the standardized ranks of change from baseline to end of treatment value in mean number of incontinence episodes per 24 hours. Treatment group and gender will be added as fixed factors in the model while the standardized ranks of mean number of incontinence episodes per 24 hours at baseline will be included as a covariate. Age group (<75 , ≥ 75) will be included as the stratification factor. LS means and two-sided 95% CIs for mean changes from baseline within each treatment group will be provided using an ANCOVA model with the same dependent and independent variables but not using the rank scale for the mean number of incontinence episodes data.

7.4.2 Secondary Analysis of Primary Endpoints

Residual plots will be produced to check the assumptions of the underlying statistical models for mean number of micturitions and incontinence episodes per 24 hours. If the fit of the models is questionable, the dependent variable may be logarithmically transformed in order to improve the fit or a non-parametric analysis could be applied as a secondary analysis. Outliers are defined and handled per section 7.10.2. If outliers are present, then additional sensitivity analyses will be performed with the outliers excluded to assess their impact on the results.

The analysis of the primary variables will be performed for Visits 3, 4 and 5. The statistical tests applied will be the same as the test applied to the ones described in Section 7.4.1.

All primary analyses will be repeated for the PPS which is considered secondary. These will be performed to assess the robustness of the primary analysis findings.

Responder Analysis for Incontinence Episodes and Improvement in Patient Perception of Bladder Condition

Two responder analyses based on incontinence episodes and two responder analyses based on PPBC will be performed at weeks 4, 8, 12, and EoT using a logistic regression model including the same factors as the ANCOVA model. Odds ratios that compare treatment effect between Mirabegron and placebo will be reported with 95% CIs and p-values.

The four responder definitions are as follows:

- Zero Incontinence Episodes: A responder is defined as a subject with 0 incontinence episodes post-baseline.
- Reduction in Incontinence Episodes: A responder is defined as a subject with $\geq 50\%$ decrease from baseline in mean number of incontinence episodes per 24 hours.

Responder Analysis for Less than 8 micturitions

A responder analyses based on less than 8 micturitions will be performed at weeks 4, 8, 12, and EoT using a logistic regression model including the same factors as the ANCOVA model. Odds ratios that compare treatment effect between Mirabegron and placebo will be reported with 95% CIs and p-values.

Sub-group Analysis

Sub-group analysis of the co-primary endpoints will be conducted using ANCOVA models with an interaction term. The interaction terms will be the treatment arm and the subgroup. These subgroup analyses will only be performed for baseline to EoT. Please see [Section 7.8](#) for the categories of the subgroups of interest.

The sub-groups to be considered for the analysis will include:

- Age group
- Race
- Gender

The models for the sub-group analysis will have the treatment arm, subgroup and baseline values as the independent variables in the model. LS means, two-sided 95% CIs, and p-values for mean changes from baseline within each subgroup will be provided.

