5.3 Efficacy

5.3.1 Patient Diary - Micturition and Incontinence

During the study, subjects will be requested to complete a 'Subject diary' which will be implemented on an electronic handheld device. This diary will collect data on micturition and incontinence. The information from the diaries will be used to evaluate the efficacy of treatment. Therefore, subjects will receive full instructions and training on how to complete the diary at Visit 2 (Placebo Run-In) and will be counseled on the importance of completing the diaries prior to the next visit. The training diary will be reviewed with the subject by the Investigator or designee to ensure accuracy and completion. The diaries and questionnaires will be reviewed during each visit after Visit 2 (Placebo Run-In) by the Investigator or designee to ensure accuracy of completion.

Diaries will be completed 3 consecutive days prior to each visit: Baseline (Visit 3), Week 4 (Visit 4), Week 8 (Visit 5), and Week 12/End of Treatment (Visit 6). During this activity, the subject will not come to the clinic for a visit. Site staff will contact the subject 3 days prior to the scheduled Visit to remind the subject they need to complete the electronic diary, review completion instructions and review changes to concomitant medications and adverse events (if applicable).

A diary day starts at midnight and ends at midnight the following day. Time to bed with intention to sleep, time to awake with intention of staying awake, type of episode (urination/incontinence), time of episode, urgency severity (see Section 5.3.4), measure of urine volume voided, and sleep interruption will be recorded by the subject in the micturition diary.

At Visit 3, diary data, including the frequency of micturition (urination episodes) urgency episodes (grade 3 and 4) and incontinence episodes per 24 hours, will be reviewed to confirm inclusion criteria.

Micturitions will be counted as only urination episodes and not episodes of incontinence.

In addition to the micturition information, the electronic diary will also collect time of medication intake.

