7.10 Handling of Missing Data, Outliers, Visit Windows, and Other Information

For efficacy variables and vital sign data, analysis at End of Treatment will take into account subjects who withdraw before Week 12 and therefore do not have measurements available for that visit. The End of Treatment analysis is a LOCF (last observation carried forward) approach.

Other imputation rules to account for missing data will be described in the SAP.

Subjects do not always adhere strictly to the visit timing in the protocol. Visit windows around the target days for each visit will be defined in the SAP.

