7 STATISTICAL METHODOLOGY

7.1 General Considerations

In general, baseline is defined as the last measurement before the first dose of double-blind study drug. For variables based on the micturition diary, the 3 days of the diary recorded prior to the baseline visit will be used to derive these variables at baseline just as the 3 diary days before each post-baseline visit will be used to derive these variables at these visits.

The End of Treatment (EoT) visit is defined as the last post-baseline visit at the end of the double-blind treatment period for which data is available. The EoT visit value for diary variables is the average or number of the diary measurements for Week 12, as applicable. If no Week 12 diary data measurements are available, then the last available earlier post-baseline average or number of the diary measurements within a designated visit window will be used.

For continuous variables, descriptive statistics will include the number of subjects (n), mean, standard deviation, median, minimum and maximum. When needed, the use of other percentiles (e.g. 10%, 25%, 75% and 90%) will be mentioned in the relevant section.

Frequencies and percentages will be displayed for categorical data. Percentages by categories will be based on the number of subjects with no missing data, i.e. will add up to 100%.

All statistical comparisons will be made using a two-sided test at $\alpha = 0.05$ significance level and confidence intervals will be reported with a coverage consistent with this significance level.

A step-down gatekeeping procedure will be performed to control the type I error rate at the 0.05 significance level for the multiple endpoints of the co-primary efficacy variables of change from baseline to end of treatment in mean number of micturitions per 24 hours and mean number of incontinence episodes per 24 hours and the key secondary efficacy variable of change from baseline to end of treatment in mean volume voided per micturition. The hypotheses will be tested in the following order: mean number of micturitions per 24 hours, mean number of incontinence episodes per 24 hours and mean volume voided per micturition.

All data processing, summarization, and analyses will be performed using SAS[®] Version 9.3 or higher. Specifications for table, figures, and data listing formats can be found in the TLF specifications for this study.

For the definition of subgroups of interest please refer to [section 7.8](#).

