7.1.1 Last Observation Carried Forward (LOCF)

For the efficacy diary data the EoT value will be calculated as the average or the count of the valid diary measurements reported in the last 3 valid diary days of the analysis visit window prior to EoT. For subjects who withdraw before week 12, the last available post-baseline average of the diary data measurements will be carried forward as the EoT value (LOCF).

For the non-diary efficacy data and safety data, the EoT value will be the last measurement within the week 12 visit day windows. For subjects who withdraw before week 12 the last measurement within the analysis visit window of the last available post-baseline visit will be carried forward as the EoT value (LOCF).

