7.4.3 Analysis of Secondary Endpoints

The secondary efficacy variables are:

- The change from baseline to week 4, 8, 12, and end of treatment in mean volume voided per micturition,
- Change from baseline to end of treatment in symptom bother and total health related quality of life scores as assessed by OAB-q questionnaire, and
- Change from baseline to end of treatment in PPBC.

The analysis for secondary endpoints will be performed in FAS-I and PPS population.

Change from baseline to end of treatment in mean volume voided

Change from baseline to end of treatment in mean volume voided will be tested using an ANCOVA model. The response variable will be the mean change in mean volume voided from baseline to the end of the study with treatment group, gender, and age group (<75, ≥ 75) as fixed factors and baseline mean volume voided as the covariate in the model. As part of the ANCOVA results, LS means and two-sided 95% CIs for mean changes from baseline within each treatment group will be provided. Differences in LS means between Mirabegron and placebo will be derived together with 95% CIs and p-values.

Sensitivity analysis

As a sensitivity analysis, a non-parametric test will be applied in investigating mean voided volume. Differences in change from baseline to end of treatment in mean volume voided per micturition between Mirabegron and placebo will be analyzed using a stratified rank ANCOVA model. The response variable will be the standardized ranks of the change from baseline to end of treatment in mean volume voided per micturition. Treatment group and gender will be fixed factors in the model while the standardized ranks of the baseline mean

volume voided per micturition will be included as covariate. Age group (<75, \geq 75) will be included as the stratification factor.

Change from baseline in symptom bother and total health related quality of life scores as assessed by OAB-q questionnaire.

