7.4.5 Analysis of Other Variables

The analysis of change from baseline scores (to weeks 4, 8, 12, and EoT) for the following additional efficacy endpoints will be analyzed in the same way as described for the mean number of micturitions (ANCOVA), with the exception of urgency incontinence episodes which will be analyzed using a stratified rank ANCOVA.

- Change from baseline in mean number of urgency episodes (grade 3 and/or 4)/24 hour
- Change from baseline in mean number of urgency incontinence episodes/24 hour
- Change from baseline in mean level of urgency
- Change from baseline in mean number of pads
- Change from baseline in mean number of nocturia episodes/24 hour
- Change from baseline in OAB-q subscale scores
- Change from baseline in TS-VAS
- Change from baseline in UAB-LSA
- Change from baseline in VES-13.

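### The by-visit analysis of the co-primaries names Visits 3, 4 and 5, so it tests baseline against itself and leaves out Week 12

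*SAP*

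**What the plan says.** For the co-primary variables, SAP 7.4.2 states: "The analysis of the primary variables will be performed for Visits 3, 4 and 5". The tests are to be those of the primary analysis: ANCOVA for micturitions and stratified rank ANCOVA for incontinence episodes. Protocol 7.4.1.2 contains the same sentence.

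The visit numbers are fixed elsewhere. Protocol 5.3.1 lists the diary visits as "Baseline (Visit 3), Week 4 (Visit 4), Week 8 (Visit 5), and Week 12/End of Treatment (Visit 6"). SAP 6.1.3.1 gives the same list, and SAP 3.3 places randomization at Visit 3.

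For other variables the SAP lists Week 12 separately from EoT:

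- **Responder analyses (7.4.2):** for example, "A responder analyses based on less than 8 micturitions will be performed at weeks 4, 8, 12, and EoT".
- **Mean volume voided (7.4.3):** "The change from baseline to week 4, 8, 12, and end of treatment in mean volume voided per micturition".
- **Other efficacy variables (7.4.5):** "The analysis of change from baseline scores (to weeks 4, 8, 12, and EoT").

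EoT differs from Week 12. Protocol 7.10 says: "The End of Treatment analysis is a LOCF (last observation carried forward) approach". SAP 7.1.1 says that for subjects who withdraw before Week 12, "the last available post-baseline average of the diary data measurements will be carried forward as the EoT value". SAP 7.1 has a matching fallback, which begins: "If no Week 12 diary data measurements are available, then the last available earlier post-baseline average".

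**The concern.** Read against the visit schedule, the sentence asks for a treatment comparison of change from baseline at baseline, and it stops at Week 8. The two most important continuous variables are then the ones without a Week 12 analysis of their own.

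At stake is a robustness check. A Week 12 result on the co-primary scale, set beside EoT, would show how far the primary result depends on carried-forward values. The other checks that SAP 7.4.2 names for the co-primaries are residual plots with a possible transformation or non-parametric analysis, outlier exclusion, and a repeat in the per-protocol set (PPS). None of these isolates carry-forward.

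The text can also be repaired in two ways: renumber to Visits 4 to 6, or drop Visit 3 and keep Weeks 4 and 8. The outputs differ. If this is settled only after unblinding, a Week 12 analysis could not be called clearly pre-specified.

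**Working it through.** **1. The plan's own figures.** The documents give no figure for the by-visit analysis. Their sample-size figures concern EoT and reproduce within 2 percentage points.

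- Micturitions: two-sided t-test, 340 per arm, difference 0.796, SD 2.7, alpha 0.05. Power is 97.0% (plan: 97%).
- Incontinence: the seven categories give P = 0.5632 (plan: 56.3%). Φ(√(3 × 680) × 0.063 − 1.96) = 81.2% (plan: 82%).
- Both, if independent: 0.970 × 0.812 = 78.8% (plan: 80%; its own rounded inputs give 0.97 × 0.82 = 79.5%).
- Enrolment per arm: 340 / (1 − 0.15) = 400, as planned.

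**2. Visits mapped to weeks.**

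| Visit | Week | In the by-visit list? | Usable test? |
|---|---|---|---|
| 3 | Baseline | Yes | No |
| 4 | 4 | Yes | Yes |
| 5 | 8 | Yes | Yes |
| 6 | 12 | No | Not named |

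The count is 2 endpoints × 3 visits = 6 tests. Of these, 2 × 1 = 2 are void and 2 × 2 = 4 are usable. With Visits 4, 5 and 6 there would be 6 tests, none void.

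**3. Can the Visit 3 test be computed?** The SAP ANCOVA was fitted to 680 simulated subjects with change set to zero. The residual sum of squares is 0, all coefficients are 0 and the t statistics are undefined. The ranks of change have zero variance, so the rank ANCOVA also fails.

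**4. Is Week 12 supplied elsewhere?** SAP 7.1.2 gives the ANCOVA for post-baseline visits in general and names no week. The count model (SAP 7.1.4 and 7.4.3) names no Week 12 analysis. The Week 12 responder analyses are binary.

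**5. How far can EoT and Week 12 differ?** Let f be the fraction carried forward, the same in both arms.

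EoT difference = (1 − f) × Week 12 difference + f × difference among carried-forward subjects

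Assume that all dropouts are carried forward and that completers show the planned 0.796.

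| f | Per arm | Difference if carried forward | EoT difference | Gap |
|---|---|---|---|---|
| 0.15 (plan minimum) | 0.15 × 400 = 60 | 0.796 | 0.796 | 0 |
| 0.15 | 60 | 0 | 0.85 × 0.796 = 0.677 | 0.119 |
| 0.20 (assumed) | 0.20 × 400 = 80 | 0 | 0.80 × 0.796 = 0.637 | 0.159 |

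**6. Does the PPS repeat cover the gap?** In part. SAP 5.2 requires completion of the study, and criterion 12 of Table 3 (SAP 5.2.1) lists an incomplete EoT diary. But the Table 3 criteria only may exclude, EoT means the last visit with data (SAP 7.1), and the PPS also removes other deviators.

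Criterion 1 excludes only treatment under 53 days. Under SAP 7.10.3.1 the Week 12 window opens on Day 71 and two valid diary days are needed, so the second falls on Day 72 at the earliest. Diary days more than 7 days after last dose are dropped, so last dose must be on Day 72 − 7 = 65 or later. Subjects treated for 53 to 64 days therefore pass criterion 1 but cannot have a Week 12 diary value. The boundary can move by a day if first dose is not on the Visit 3 date.

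**The case against.** The strongest reply is that this is a stale visit number and nothing was left out of the plan. SAP 7.10.1.1 calls the randomization visit Visit 2; on that numbering Visits 3 to 5 are Weeks 4, 8 and 12. Criterion 2 of SAP Table 3 also has a stray Visit 2, and SAP 7.1.2 defines the ANCOVA only for post-baseline visits, so a programmer should notice. That is the likely explanation, but it is an inference from stray labels and the text still needs correcting.

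Other points on that side:

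- **EoT equals Week 12 for anyone with a Week 12 diary value (SAP 7.1).** True. The gap concerns only subjects with a carried-forward value.
- **The Week 12 responder analyses do not use LOCF.** SAP 7.10.1 sets non-responder imputation for binary endpoints. This gives partial cover, but not on the co-primary scale.
- **The illustration may overstate the gap.** Protocol 2.2.2 says the effect at Week 4 is already near its maximum, which favours the low end. The 0.796 was used to size the EoT endpoint, so giving it to Week 12 completers is an assumption. The full analysis set (SAP 5.1) requires a post-baseline micturition, so some early dropouts contribute no carried-forward value. All three points stand, and 60 per arm is a ceiling at 15% dropout.
- **The 53-to-64-day PPS point is conditional.** It applies only if PPS membership is decided on Table 3 alone, without the completion requirement.
- **An observed Week 12 analysis also changes who is analysed.** True. It checks dependence on carry-forward but does not isolate it cleanly.

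The table specifications are not available. They may list Week 12, but that would not correct the SAP.

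**Conclusion.** The concern holds. As written, 2 of the 6 by-visit co-primary tests cannot be computed, and no Week 12 analysis of change in micturitions or incontinence episodes is named in either document. This follows from the text and the visit schedule and needs no assumption.

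The consequence is limited. The primary EoT tests, the gatekeeping order, alpha control and sample size are intact. What is missing is a secondary result to set beside a LOCF-based primary result. Under the stated assumptions the two could differ by 0 to 0.12 micturitions per 24 hours at 15% dropout, or up to 0.16 at 20%. These figures are not predictions, since dropout timing and the effect in carried-forward subjects are not given. The correction should be made, but it does not threaten the trial's main conclusion.

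**What to change.** In SAP 7.4.2, name Visits 4, 5 and 6 (Weeks 4, 8 and 12), keep the same ANCOVA and stratified rank ANCOVA, and report Week 12 next to EoT. State that the by-visit analyses use observed data without LOCF. SAP 7.10.1 applies LOCF to missing continuous efficacy endpoints in broad terms, and read literally it could turn Week 12 back into EoT. Describe the Week 12 result as a check on dependence on carried-forward values, and note that it also changes the set of subjects analysed.

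If protocol 7.4.1.2 is left as it is, add a note that the SAP's visit list replaces it. SAP 7.5.3 already handles an omission in the protocol in this way. As housekeeping, align the stray Visit 2 labels in criterion 2 of SAP Table 3 and in SAP 7.10.1.1.

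The cost is one sentence and one note in the SAP, plus one visit added to existing programs, with no new data. SAP section 1 allows revision before database hard lock; after that, the change would have to be justified in the study report. Changing the protocol sentence would need a signed amendment (protocol 8.3.3), but the SAP correction is enough.
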